### **5. SUBJECT SELECTION**

#### **5.1. STUDY POPULATION**

A total of 24 male and female subjects will be enrolled in the study.

#### **5.2. INCLUSION CRITERIA**

Each subject must comply with the following criteria:

1. Male or female subjects between 18 and 45 years of age, inclusive.
2. The subject has a body mass index (BMI) within 18-30 kg/m^2 (inclusive).
3. The subject is in good health as determined by medical history and physical examination and clinical laboratory parameters.
4. The subject is willing and able to speak, read, and understand English and provide written informed consent.
5. The subject is a non-smoker for at least 12 months. If a former smoker, the reason for stopping must be evaluated.
6. Females who are physically incapable of childbearing defined as postmenopausal, or surgically sterile (hysterectomy, bilateral tubal ligation, bilateral oophorectomy or an Essure procedure). Appropriate documentation (ex; medical record) of the surgical sterilization procedure to be obtained and held within the subject's study file.
7. The subject must agree to comply with the drawing of blood samples for the PK assessments.
8. The subject is willing and able to comply with all testing and requirements defined in the protocol.
9. The subject is willing and able to remain at the study site unit for the duration of the confinement period and return for the outpatient visit.

### **5.3. EXCLUSION CRITERIA**

Subjects meeting any of the following criteria will be excluded from the study.

1. The subject has any relevant deviations from normal in physical examination, electrocardiogram (ECG), or clinical laboratory tests, as evaluated by the investigator.
2. The subject has had a clinically significant illness within 30 days of Check-in.
3. The subject has a history of significant neurological, hepatic, renal, endocrine, cardiovascular, gastrointestinal, pulmonary, or metabolic disease.
4. The subject has used any prescription medication within 14 days of dosing or over-the-counter (OTC) medication within 48 h of dosing or intends to use any prescription medication or OTC medication during the study that may interfere with the evaluation of study medication.
5. The subject has used alcohol, caffeine or xanthine-containing products 48 h before dosing or intends to use any of these products during the study.
6. The subject has used grapefruit, grapefruit juice, or grapefruit-containing products 7 days before dosing or intends to use any of these products during the study.
7. The subject has a history of substance abuse or a positive ethanol breath test, urine cotinine, or urine drug screen at screening or at check-in.

8. The subject has a positive serum hepatitis B surface antigen or positive HCV antibody test at the Screening Visit.
9. The subject has a positive HIV test at the Screening Visit.
10. Female subject is pregnant or breastfeeding.
11. The subject has received an investigational drug within 30 days of Check-in.
12. The subject has donated or lost a significant volume of blood (>450 mL) within 4 weeks prior to the study.
13. The subject is unwilling to reside in the study unit for the duration of the study or to cooperate fully with the investigator or site personnel.
14. The subject has an AST/ALT or total bilirubin greater than the ULN. One repeat test will be allowed.

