## 1. LIST OF ABBREVIATIONS

$\alpha$ 7nAChR	$\alpha$ 7 nicotinic acetylcholine receptor
A $\beta$ 42	amyloid beta 1-42
AD	Alzheimer's disease
AE	adverse event
ALT	alanine transaminase
ANOVA	analysis of variance
AST	aspartate transaminase
AUC	area under the curve
BMI	body mass index
BUN	blood urea nitrogen
CFR	Code of Federal Regulations
C max	maximum plasma concentration
CRF	case report form
CRO	contract research organization
DSMB/DMC	Data Safety Monitoring Board/Data Monitoring Committee
EC	ethics committee
ECG	electrocardiogram
EDTA	ethylenediaminetetraacetic acid
FDA	Federal Drug Association
FLNA	filamin A
GCP	good clinical practices
GGT	gamma glutamyl transpeptidase
GLP	good laboratory practice
HBsAg	hepatitis B surface antigen
HCV	hepatitis C virus
HIV	human immunodeficiency virus
hERG	human ether-a-go-go-related gene
ICH	International Council on Harmonisation of Technical Requirements for Registration of Pharmaceuticals for Human Use
IR	insulin receptor
IRB	independent review board
LDH	lactose dehydrogenase
LOQ	limit of quantitation
NMDA	N-methyl D-aspartate
NOAEL	no observable adverse effect level
OTC	over-the-counter
PHCG	placental human chorionic gonadotropin
PK	pharmacokinetics
PTI	Pain Therapeutics, Inc.
QS	quantity sufficient
RBC	red blood cell
SAD	single ascending dose
SAE	serious adverse event
T max	time to C max
WBC	white blood cell

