### **7.1. EVALUATIONS BY VISIT**

#### **7.1.1. *Screening Period***

The following will be completed within 29 days prior to administration of the study medication:

- Informed Consent (written consent must be obtained prior to conducting any screening activities)
- Review of Inclusion and Exclusion Criteria

- Medical history
- Review of concomitant medications
- Physical examination, including measurement of orthostatic vital signs (blood pressure, temperature, pulse and respiratory rate after a 3-min sitting period followed by blood pressure and pulse after a 2-min stand period), height, weight and calculated BMI.
- A 12-lead ECG (5-minute supine)
- Laboratory assessments, including serum chemistry, hematology, and urinalysis; ethanol breath test, urine drug screen, urine cotinine, HIV test, HBsAg and HCV Antibody.
  
- FSH test for female subjects claiming post-menopausal status

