## 7.2. LABORATORY ASSESSMENTS

### 7.2.1. *Clinical Laboratory Tests*

The following clinical laboratory tests will be performed at screening, Day 1 pre-dose, at 24 h post-dose, and at the Day 7 follow-up visit:

- Hematology: white blood cell (WBC) count with differential, red blood cell (RBC) count, hemoglobin, hematocrit, platelet count.
- Serum Chemistry: glucose, sodium, potassium, chloride, bicarbonate, blood urea nitrogen (BUN), creatinine, uric acid, phosphorus, calcium, total protein, albumin, globulin, alkaline phosphatase, alanine transaminase (ALT), aspartate transaminase (AST), gamma glutamyl transpeptidase (GGT), total bilirubin, lactose dehydrogenase (LDH).
- Urinalysis: color, specific gravity, pH, protein, sugar, ketones, occult blood, creatinine clearance calculation by Cockcroft-Gault equation.
- At screen only: FSH will be performed on all females claiming to be of post-menopausal status.

The following tests will be performed at screening and at check-in to the clinic:

- Urine drug screen: amphetamines, barbiturates, benzodiazepines, cocaine, opiates, and cannabinoids
- Urine Cotinine
- Ethanol breath test
- HIV test (screening only)
- HBsAg, HCV Antibody tests (screening only)

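### Exclusion 10 bars pregnant women, but no pregnancy test is listed at any visit, and inclusion 6 admits women who keep the uterus and ovaries

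*Combined protocol and SAP*

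**What the plan says.** Exclusion 10 in Section 5.3 applies where "Female subject is pregnant or breastfeeding". It names no test, method or time point.

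Inclusion 6 in Section 5.2 limits which women may enter: "Females who are physically incapable of childbearing defined as postmenopausal, or surgically sterile (hysterectomy, bilateral tubal ligation, bilateral oophorectomy or an Essure procedure". For the surgical routes it adds: "Appropriate documentation (ex; medical record) of the surgical sterilization procedure to be obtained and held within the subject's study file". Inclusion 1 sets the age range: "Male or female subjects between 18 and 45 years of age, inclusive".

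The only laboratory test specific to women is FSH. Section 7.1.1 lists it as "FSH test for female subjects claiming post-menopausal status", and Section 7.2.1 as "At screen only: FSH will be performed on all females claiming to be of post-menopausal status". Neither gives a threshold. Appendix A has a row for FSH and none for a pregnancy test.

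Section 7.1.2 requires the eligibility criteria to be confirmed again at check-in on Day 0. The tests listed there are the ethanol breath test, the urine drug screen and urine cotinine. Section 2 describes the study as first in human.

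**The concern.** An exclusion that depends on a biological state needs a way to establish that state. The protocol provides one for its other exclusions of this kind, but not for pregnancy. If inclusion 6 does not fully rule pregnancy out, a woman could meet every listed check, be randomised and be dosed while pregnant. Nothing later in the schedule would reveal it, because Day 7 has no pregnancy test either.

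What is at stake is participant safety, and the fetus's. The nonclinical summary in Section 2 covers ADME, safety pharmacology, and general and genetic toxicology. The supplied text describes no reproductive or developmental toxicology study.

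**Working it through.** The protocol gives no figure on this point, so there is nothing to recompute. The check is a comparison of sections.

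**1. Where a pregnancy test could be listed**

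| Place | Pregnancy test | Other tests bearing on eligibility |
|---|---|---|
| 7.1.1 Screening | None | Laboratory panel, ethanol, drug screen, cotinine, HIV, HBsAg, HCV, FSH (claimed menopause) |
| 7.1.2 Check-in, Day 0 | None | Ethanol, drug screen, cotinine |
| 7.1.2 Day 1 to 72 h | None | Laboratory panel before dosing and at 24 h |
| 7.1.3 Day 7 | None | Laboratory panel |
| 7.2.1 Laboratory list | None | All of the above |
| Section 8 Early discontinuation | None | Laboratory panel |
| Appendix A | None in any of its 6 visit columns | FSH, HIV, hepatitis, cotinine, drug and ethanol rows |

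The screening list, the laboratory list and Appendix A are separate places. All three carry FSH and the infection and substance tests, and none carries hCG. A table damaged in text extraction would not explain the absence from all three.

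**2. How comparable exclusions are written**

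- Exclusion 7 names the breath test, urine cotinine and urine drug screen, at screening or check-in.
- Exclusions 8 and 9 name the hepatitis and HIV tests at screening.
- Exclusion 14 names AST/ALT and total bilirubin, and allows one repeat.
- Exclusion 10 names nothing.

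**3. What each route through inclusion 6 provides**

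| Route | Evidence required | Uterus and ovaries both in place? | FSH | hCG |
|---|---|---|---|---|
| Hysterectomy | Procedure record | No | No | No |
| Bilateral oophorectomy | Procedure record | No | No | No |
| Bilateral tubal ligation | Procedure record | Yes | No | No |
| Essure | Procedure record | Yes | No | No |
| Postmenopausal, age at most 45 | FSH once at screening, no threshold | Yes | Yes | No |

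The anatomical column is general knowledge; the documents do not state it. For the first two routes the record settles the matter. For tubal ligation and Essure, the record shows that a procedure was done but does not measure whether the woman is pregnant now. For claimed menopause, the FSH result is left to the investigator's judgement.

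**4. Timing**

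Screening may take place up to 29 days before dosing (Section 7.1.1). Status established at screening is therefore not necessarily status at dosing, and check-in adds no measurement to update it.

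**The case against.** The strongest defence is that pregnancy risk is controlled through eligibility. Women of childbearing potential, as the protocol defines it, are not admitted at all, so a pregnancy test would be a second safeguard. This has force, and it is why the probability is low. It does not make the test redundant. Two of the four surgical routes leave conception anatomically possible. The protocol also keeps exclusion 10 alongside inclusion 6, which treats pregnancy as something still to be excluded.

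Some stronger readings are tempting, but the documents do not support them:

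- *The exclusion rests on self-report.* It does not. Sterilisation must be documented, claimed menopause is checked by FSH, and there are a medical history and a physical examination.
- *The FSH result has no bearing on eligibility.* Inclusion 6 itself requires postmenopausal status, and exclusion 1 lets the investigator exclude for relevant laboratory deviations. What is missing is a threshold, which is a smaller point.
- *Fetal risk is uncharacterised.* Section 2 is an introductory summary, and the Investigator's Brochure is not among the documents. All that can be said is that no reproductive or developmental study is described here.
- *A planned test was dropped.* The abbreviation list defines PHCG as "placental human chorionic gonadotropin", and the term is not used again in the supplied text. LOQ and QS are also defined there and not used, so leftover template text is an equally good explanation.
- *Every woman needs testing.* After a documented hysterectomy or bilateral oophorectomy, a test adds nothing useful.

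**Conclusion.** The point holds as a gap in ascertainment: exclusion 10 has no matching test at any visit. Pregnancy tests planned per woman number 0 at screening and 0 at check-in. The women concerned are those entering by tubal ligation, Essure or claimed menopause; those in the first two groups have no FSH either. How many there will be is not fixed, because the protocol plans 24 male and female subjects without stating a split.

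The documents give no failure rate for the sterilisation procedures, so an expected number of undetected pregnancies cannot be computed. It should be taken as low, and exposure is a single dose. No estimate, sample size or analysis is touched. The case for acting is that a site can carry out every listed procedure and still dose a pregnant woman undetected in a first-in-human study, and that closing the gap costs little.

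The conclusion assumes that the documents supplied contain the full list of procedures. The consent appendix and the Investigator's Brochure were not available to check.

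**What to change.** For female subjects without documented hysterectomy or bilateral oophorectomy, add an hCG test at screening and again at Day 0 check-in, and require a negative result before randomisation. Enter it in Sections 7.1.1, 7.1.2 and 7.2.1 and as a row in Appendix A. Reword exclusion 10 so that pregnancy is defined by a positive hCG at either visit, in the way that exclusion 7 is tied to its tests; the breastfeeding part can stay as it is.

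Urine is already collected at both visits for the drug and cotinine screens, so no new visit or sample is needed. The cost is one extra inexpensive assay at each of the two visits and an occasional repeat for a false positive.

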## **6. STUDY DRUG**

### **6.1. PTI-125 PHYSICAL DESCRIPTION AND PREPARATION**

Investigational PTI-125 will be supplied by PTI as the bis-HCl monohydrate salt solid form and buffer components. An on-site pharmacist will mix a 50 mg/ml solution (free base equivalent) in pH 5.2, 0.3 M citric acid / citrate buffer following the study-specific pharmacy manual, PTI-125 Clinical Dosing Instructions. To achieve 50 mg, 100 mg, and 200 mg dosing solutions, 1, 2 or 4 ml drawn into a 5-ml syringe will be mixed with 15 ml of ORA-sweet SF drawn into a 20-ml syringe using a syringe connector as specified in the manual. After mixing, each dose will be contained in the 20-ml syringe and appropriately labeled. Further details on dose preparation and administration are found in PTI-125 Clinical Dosing Instructions. Placebo will be 15 ml ORA-sweet SF mixed with 1, 2 or 4 ml pH 5.2, 0.3 M citric acid / citrate buffer.

All containers, syringes or bottles of PTI-125, used or unused, will be saved for final disposition by the sponsor or designee.

#### **6.1.1. Storage**

The bottles and syringes of PTI-125 prior to dissolving and as a solution must be stored at refrigerated conditions (2° C – 8° C). PTI-125 in solution can be kept at room temperature prior to dosing up to 4 h.

#### **6.1.2. Drug Accountability**

The Investigator will be responsible for monitoring the receipt, storage, dispensing and accounting of all study medications according to site SOPs. All invoices of study medication shipments must be retained in the site study file. Accurate, original site records must be maintained of drug inventory and dispensing. All

records must be made available to the sponsor (or designee) and appropriate regulatory agencies upon request.

## **6.2. ADMINISTRATION AND DOSING REGIMEN**

All subjects in each cohort (8 subjects) will be randomized to receive PTI-125 (6 subjects) or placebo (2 subjects). Following an overnight fast of at least 10 h, subjects will receive a single oral dose of PTI-125 oral solution or placebo followed by approximately 240 mls of room temperature water. No food will be allowed until 4 h post-dose. Water will be allowed as desired except for 1 h before and 1 h after dosing.

## **6.3. CONCOMITANT MEDICATIONS**

Use of prescription medications will be prohibited for 14 days before initial drug administration and during the study. Non-prescription medications will be prohibited for 48 h before initial drug administration and during the study.

Use of alcohol and caffeine- or xanthine-containing products is prohibited for all subjects 48 h before dosing and during the study.

Use of grapefruit, grapefruit juice, and grapefruit-containing products is prohibited for all subjects 7 days before dosing and during the study.

## **7. STUDY PROCEDURES**

Appendix A presents the Schedule of Activities.

Prior to any study-related activities, the Informed Consent Form must be signed and dated by the subject. The format and content of the Informed Consent Form must be agreed upon by the Principal Investigator(s), the appropriate IRB and the Sponsor (or designee). Appendix B contains a sample Informed Consent for this study. The signed and dated Informed Consent Form must be retained by the Investigator in the subject's file.

### **7.1. EVALUATIONS BY VISIT**

#### **7.1.1. *Screening Period***

The following will be completed within 29 days prior to administration of the study medication:

- Informed Consent (written consent must be obtained prior to conducting any screening activities)
- Review of Inclusion and Exclusion Criteria

- Medical history
- Review of concomitant medications
- Physical examination, including measurement of orthostatic vital signs (blood pressure, temperature, pulse and respiratory rate after a 3-min sitting period followed by blood pressure and pulse after a 2-min stand period), height, weight and calculated BMI.
- A 12-lead ECG (5-minute supine)
- Laboratory assessments, including serum chemistry, hematology, and urinalysis; ethanol breath test, urine drug screen, urine cotinine, HIV test, HBsAg and HCV Antibody.
  
- FSH test for female subjects claiming post-menopausal status

#### 7.1.2. *In-patient Period - Study Days 0-4*

**Note:** Study Day 1 is defined as the day of dosing for each dose cohort.

Subjects will check into the clinic at the designated time on Day 0, and will remain confined to the clinic until Study Day 4. Upon check-in, the following assessments will be conducted:

- Confirmation of inclusion/exclusion criteria
- Ethanol breath test
- Urine drug screen
- Urine Cotinine test
- Review of concomitant medications
- Orthostatic vital signs (blood pressure, temperature, pulse and respiratory rate after a 3-min sitting period followed by blood pressure and pulse after a 2-min stand period).
- Brief physical examination

Following a supervised fast for at least 10 h, subjects will be administered a single oral dose of study drug (or placebo) on Study Day 1.

The appropriate dosing syringe of PTI-125 or placebo (15 ml ORA-sweet SF mixed with 1, 2 or 4 ml pH 5.2, 0.3 M citric acid / citrate buffer) mixed with ORA-sweet SF for taste masking will be administered. Subjects will also consume water provided as a rinse of the dosing syringe, to ensure complete consumption of study drug.

No food will be allowed for 4 h post-dose. Water will be allowed as desired except for 1 h before and 1 h after dosing. At 4 h post-dose, subjects will be provided a standard lunch.

On the morning of Study Day 1, within 30 min prior to dosing, the following assessments will be conducted:

- Orthostatic vital signs (blood pressure, temperature, pulse and respiratory rate after a 3-min sitting period followed by blood pressure and pulse after a 2-min stand period).
- Review of concomitant medications
- Blood sample collection for baseline PK assessment (Sample Time=0)
- On Day 1, blood sample collection for laboratory testing prior to dosing (Time=0)
- ECG (Time=0)

After dose, the following assessments will be conducted:

- Orthostatic vital signs (blood pressure, temperature, pulse and respiratory rate after a 3-min sitting period followed by blood pressure and pulse after a 2-min stand period) at approximately 10 and 30 minutes, and 1, 2, 3, 4, 8, 12, 24, 36, 48 and 72 h post-dose.
- Blood samples will be drawn at 20, 40, and 60 min following dosing and at 2, 3, 4, 6, 8, 12, 24, 36, 48 and 72 h for PK assessments
- Adverse event monitoring
- Clinical laboratory tests at approximately 24 h post-dose
- Brief physical examination at approximately 24 and 72 h post-dose
- ECG at approximately 30 min, and 1, 2, 3, 4, 8, 12, 24, 36, 48 and 72 h post-dose.

Should procedures occur at the same nominal timepoint collection of the PK assessment will take priority. All other procedures will be performed within a sufficient +/- window for logistical purposes.

All subjects will receive a standardized lunch 4 h post-dose. All subsequent meals will be served at standard meal times.

Clinic personnel will monitor the subjects for the occurrence of any adverse events until subjects are discharged from the clinic. Subjects will be discharged from the clinic upon investigator judgment after results of all safety assessments following the last dose have been reviewed.

### **7.1.3. Follow-up Visit – Study Day 7**

At the Day 7 follow up visit, the following assessments will be conducted:

- Orthostatic vital signs (blood pressure, temperature, pulse and

respiratory rate after a 3-min sitting period followed by blood pressure and pulse after a 2-min stand period)

- ECG
- Adverse event monitoring
- Physical examination
- Clinical laboratory tests

## 7.2. LABORATORY ASSESSMENTS

### 7.2.1. *Clinical Laboratory Tests*

The following clinical laboratory tests will be performed at screening, Day 1 pre-dose, at 24 h post-dose, and at the Day 7 follow-up visit:

- Hematology: white blood cell (WBC) count with differential, red blood cell (RBC) count, hemoglobin, hematocrit, platelet count.
- Serum Chemistry: glucose, sodium, potassium, chloride, bicarbonate, blood urea nitrogen (BUN), creatinine, uric acid, phosphorus, calcium, total protein, albumin, globulin, alkaline phosphatase, alanine transaminase (ALT), aspartate transaminase (AST), gamma glutamyl transpeptidase (GGT), total bilirubin, lactose dehydrogenase (LDH).
- Urinalysis: color, specific gravity, pH, protein, sugar, ketones, occult blood, creatinine clearance calculation by Cockcroft-Gault equation.
- At screen only: FSH will be performed on all females claiming to be of post-menopausal status.

The following tests will be performed at screening and at check-in to the clinic:

- Urine drug screen: amphetamines, barbiturates, benzodiazepines, cocaine, opiates, and cannabinoids
- Urine Cotinine
- Ethanol breath test
- HIV test (screening only)
- HBsAg, HCV Antibody tests (screening only)

### 7.2.2. *Preparation of Plasma Samples for Pharmacokinetic Determination*

At each blood collection, blood samples (4 mL) will be drawn into a Vacutainer® tube containing K2EDTA. The tubes will be placed on ice. Within 30 minutes of collection, the blood will be centrifuged at approximately 1000 X G for 15 minutes between 4-5°C. Within 30 minutes of centrifuging, plasma (at least 1.5 mL) will be split evenly into two aliquots, transferred to polypropylene tubes and stored at

approximately -70°C or below until analysis. The time from sample collection to storage should not exceed 60 minutes.

At the end of the study the samples will be shipped frozen on dry ice to: Worldwide Clinical Trials Bioanalytical Sciences, [name] for bioanalytical analysis of PTI-125 with a validated assay. Remaining samples following the analysis of PTI-125 are to be retained until directed for disposition by PTI. All samples from PTI-125 subjects will be analyzed. One sample around the Cmax from each placebo subject will be analyzed, such as 40 min, 1 or 2 h. All secondary samples will be shipped to Worldwide Clinical Trials Bioanalytical Sciences upon confirmation of receipt of the primary samples.

